# 10.2.2 Exposure adjusted incidence rate (EAIR) and exposure adjusted event rate (EAER)

Selected AE summaries will include the EAIR with associated 95% confidence interval and EAER where the EAIR and EAER are expressed per 100 study participant-years of exposure.

The EAIR is defined as the number of participants (n) with a specific AE adjusted for the exposure and will be scaled to 100 study participant-years:  $EAIR = 100 \times \frac{n}{\sum_{i=1}^{N} (T_{EXP(i)})}$ 

where n is the total number of participants with AE of interest, N= number of participants at risk of an AE, and  $T_{Exp(i)}$  is the total exposure time for each participant:

- For participantss with the specific AE of interest:time at risk in years to the first occurrence for the AE of interest at the level of coding evaluated
- For participantss without the AE: the total time at risk in years.

Exact Poisson 95% confidence intervals for incidence rates are calculated using the relationship between the Poisson and the Chi-square distribution (Ulm, 1990; Fay and Feuer, 1997):

$$LCL = \frac{x_{2n,\alpha/2}^2}{2}$$

$$UCL = \frac{x_{2(n+1),1-\alpha/2}^2}{2}$$

Confidential Page 39 of 89

UCB Statistical Analysis Plan 03 Mar 2023 OP0002

where n is the number of participants with a specific AE for the incidence rate of interest and is the basis for the number of the degrees of freedom for the chi-square quantile for the upper tail probability  $\chi 2$ .

The EAER will be the number of AEs including repeat occurrences in individual participants divided by the total time at risk scaled to 100 study participant-years and calculated using:

$$EAER = 100 \times \frac{N_{AE}}{\sum_{i=1}^{N} (T_{Risk(i)})}$$

where is the total number of AEs, n is the total number of participants and  $T_{Risk(i)}$  is the time at risk in years for each participant for each exposure period.

No confidence interval will be computed for EAER.

The following summaries will be provided by actual treatment group for the DBPC and the Overall Periods based on the SS. In addition, all summaries of TEAEs based on "100 participant-years" will include EAIR (with 95% confidence interval) and EAER.

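### The confidence limits printed for the exposure-adjusted incidence rate are limits for the event count, so an interval can exclude its own rate

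*SAP*

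**What the plan says.** SAP 10.2.2 announces selected adverse event summaries with an EAIR, its 95% interval and an event rate (EAER), "where the EAIR and EAER are expressed per 100 study participant-years of exposure". The EAIR is 100 × n / ΣT_EXP. For a participant with the event, exposure stops at the first occurrence; for the others it is the whole time at risk.

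On the interval, the section says: "Exact Poisson 95% confidence intervals for incidence rates are calculated using the relationship" between the Poisson and chi-square distributions. It prints

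- LCL = χ²(2n, α/2) / 2
- UCL = χ²(2(n+1), 1−α/2) / 2

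The legend reads: "where n is the number of participants with a specific AE for the incidence rate of interest". It adds that n sets the "degrees of freedom for the chi-square quantile for the upper tail" probability. It does not mention exposure. The same section requires the EAIR with its interval in all treatment-emergent adverse event (TEAE) summaries per 100 participant-years. SAP 10.2.3 lists three such displays, all for the overall period: the overview, the table by system organ class and preferred term, and the serious events.

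**The concern.** The point estimate "will be scaled to 100 study participant-years", but its limits are not. Both limits depend on n and α alone, so an interval labelled as one for a rate is built on the scale of a count. I found no step elsewhere in the SAP or protocol that converts it.

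Two groups with the same number of affected participants would receive identical intervals, although exposure to romosozumab in the overall period differs about fourfold between the randomized groups. The printed limits are too high where exposure exceeds 100 PY and too low where it is below. That removes the exposure adjustment from the interval in the tables that report the primary safety variable, the overall incidence of TEAEs.

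**Working it through.** The SAP prints a formula and no numerical interval, so there is no stated figure to reproduce.

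**1. What the printed limits are.** With α = 0.05 and lower-tail quantiles, write L(n) = χ²(0.025; 2n)/2 and U(n) = χ²(0.975; 2n+2)/2.

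| n | L(n) | U(n) |
|---|---|---|
| 2 | 0.24 | 7.22 |
| 5 | 1.62 | 11.67 |
| 10 | 4.80 | 18.39 |
| 20 | 12.22 | 30.89 |
| 40 | 28.58 | 54.47 |

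Checked against the Poisson distribution for counts from 1 to 100, P(X ≥ n) = 0.025 at mean L(n) and P(X ≤ n) = 0.025 at mean U(n). These are the exact limits for the mean count. The limits for a rate per 100 PY are 100·L(n)/T and 100·U(n)/T, with T = ΣT_EXP. The two sets agree only when T = 100.

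**2. Exposure.** The documents give no person-years, so T is an assumption, shown as a range.

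- Arms are 200 and 100 (SAP 2.6) and a month is 30 days (Protocol 8).
- SAP 10.2.1 runs time at risk from first to last romosozumab, plus 1 day, divided by 365.25. The end point could be the last dose date or that date plus a dosing interval.
- Twelve months of romosozumab is then 11 × 30 + 1 = 331 days, or 360. Six months is 5 × 30 + 1 = 151 days, or 180.
- No dropout and no cut at first event at this stage.

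Romosozumab/romosozumab: 200 × 331 / 365.25 = 181.2 PY, or 200 × 360 / 365.25 = 197.1 PY. Placebo/romosozumab: 100 × 151 / 365.25 = 41.3 PY, or 100 × 180 / 365.25 = 49.3 PY.

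**3. Printed against rescaled limits.**

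| Group | T (PY) | n | EAIR = 100n/T | As printed | Rescaled by 100/T |
|---|---|---|---|---|---|
| Romosozumab/romosozumab | 181.2 | 20 | 11.03 | 12.22–30.89 | 6.74–17.04 |
| Romosozumab/romosozumab | 197.1 | 20 | 10.15 | 12.22–30.89 | 6.20–15.67 |
| Placebo/romosozumab | 41.3 | 10 | 24.19 | 4.80–18.39 | 11.60–44.48 |
| Placebo/romosozumab | 49.3 | 10 | 20.29 | 4.80–18.39 | 9.73–37.32 |
| Placebo/romosozumab | 41.3 | 2 | 4.84 | 0.24–7.22 | 0.59–17.48 |

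In the first four rows the printed interval excludes the estimate. In the last it contains it, but the upper limit is too low by a factor of 100/41.3 = 2.4.

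**4. When exclusion occurs.** The printed interval contains the EAIR only if 100n/U(n) ≤ T ≤ 100n/L(n). For n = 10 that is 54.4 to 208.5 PY; for n = 20 it is 64.7 to 163.7 PY. At the exposures above, exclusion starts at n = 15 (T = 181.2) or 12 (T = 197.1) in romosozumab/romosozumab, and at n = 5 (T = 41.3) or 8 (T = 49.3) in placebo/romosozumab. The rescaled interval contains the estimate whenever L(n) ≤ n ≤ U(n), which held for every n from 0 to 1999.

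**5. Effect of cutting time at first event.** As an extreme, let every affected participant contribute no time.

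- Romosozumab/romosozumab, n = 20: T = 180 × 331 / 365.25 = 163.1 PY and EAIR = 12.26, just inside 12.22–30.89. The rescaled interval is 7.5–18.9.
- Placebo/romosozumab, n = 10: T = 90 × 151 / 365.25 = 37.2 PY and EAIR = 26.9, still above 18.39.

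**6. Tail wording.** If the printed subscripts are read as upper-tail areas, as the legend suggests, n = 10 gives a lower limit of 17.08 and an upper limit of 5.49.

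**The case against.** The strongest reply is that the intent is plain. The section names the scale, calls the limits intervals for incidence rates, and prints the scaling for the EAIR just above. A programmer may supply 100/ΣT_EXP without being told, and wrong tables follow only from literal coding that nobody notices. The intent is indeed clear, but it does not make the printed rule right. Two programmers working independently from this text could agree on the same wrong limits, and in rows with few events the estimate would often still lie inside the interval, so nothing would look odd.

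The romosozumab/romosozumab example is sensitive to exposure. It needs T above about 164 PY; censoring at first event, or losing 10% of person-time, brings the estimate just inside the printed limits. That stands as a limit on the example. The interval is still on the wrong scale, and the placebo/romosozumab example survives.

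The LCL and UCL labels show that lower-tail quantiles are meant, so the tail phrase is loose wording that needs tidying more than a second numerical error. No safety testing is planned (SAP 10.2.3), and point estimates, EAER, counts and percentages are untouched. All of that stands, and it limits the consequence to descriptive output.

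**Conclusion.** The concern holds. As printed, the limits in SAP 10.2.2 are exact for the expected count and are attached to a rate per 100 PY. Each limit is wrong by a factor of T/100: roughly 1.8 to 2.0 times too high in romosozumab/romosozumab, and 0.41 to 0.49 of the right value in placebo/romosozumab. At those exposures the interval excludes its own estimate from 12 to 15 affected participants in the first group and from 5 to 8 in the second.

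These figures assume full arms, no dropout and no cut at first event. Dropout and the cut both reduce T, so the thresholds are approximate. Where T is near 100 PY the error is hidden: 200 participants over 180 days of double-blind treatment give 98.6 PY. Efficacy analyses are not affected. This should be corrected before the safety tables are programmed.

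**What to change.** Replace the two formulas in SAP 10.2.2 with

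- LCL = 100 × χ²(0.025; 2n) / (2 × ΣT_EXP), with LCL = 0 when n = 0, because the quantile then has no degrees of freedom
- UCL = 100 × χ²(0.975; 2(n+1)) / (2 × ΣT_EXP)

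State that the quantiles are lower-tail and that ΣT_EXP is the same event-specific denominator used for the EAIR in that row. The cost is one formula line in the SAP and the matching line of table code. Data collection and trial conduct do not change.

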### 10.2.3 Standard AE summaries

- TEAEs overview during DBPC period
- TEAEs overview per 100 patient-years during overall period
- TEAEs by SOC and PT during DBPC period
- TEAEs per 100 patient-years by SOC and PT during overall period
- TEAEs by maximum intensity by SOC and PT during DBPC period
- TEAEs by maximum intensity by SOC and PT during overall period
- TEAEs by maximum relationship to IMP per the Investigator by SOC and PT during DBPC period
- TEAEs by maximum relationship to romosozumab per the Investigator by SOC and PT during overall period
- TEAEs leading to IMP discontinuation by SOC and PT during DBPC period
- TEAEs leading to romosozumab discontinuation by SOC and PT during overall period
- TEAEs leading to study discontinuation by SOC and PT during DBPC period
- TEAEs leading to study discontinuation by SOC and PT during overall period
- TEAEs leading to death by SOC and PT during DBPC period
- TEAEs leading to death by SOC and PT during overall period
- Serious TEAEs by SOC and PT during DBPC period
- Serious TEAEs per 100 patient-years by SOC and PT during overall period
- Serious TEAEs by maximum relationship to study medication per the Investigator by SOC and PT during DBPC period

Confidential

- Serious TEAEs by maximum relationship to study medication per the Investigator by SOC and PT during overall period
- Fatal TEAEs by maximum relationship to study medication per the Investigator by SOC and PT during DBPC period
- Non-serious TEAEs above reporting frequency threshold of 5% by SOC and PT during DBPC period

  Non-serious TEAEs above reporting frequency threshold of 5% by SOC and PT during DBPC period
- Non-serious TEAEs above reporting frequency threshold of 5% by SOC and PT during overall period

  TEAEs of interest by SOC and PT during DBPC period

  TEAE of special interest (PDILI) by SOC and PT during DBPC period

- TEAE of special interest (PDILI) by SOC and PT during DBPC period
- TEAEs of special interest (PDILI) by SOC and PT during overall period
- TEAEs of COVID-19 vaccine by SOC and PT during DBPC period

TEAEs of COVID-19 vaccine by SOC and PT during overall period There is no planned statistical testing in the safety analyses.

#### 10.2.4 Adverse events of interest

Subject incidence of adverse events of interest of hypocalcemia, injection site reactions, potentially related to hypersensitivity (Standardized MedDRA® Query [SMQ], narrow scope), malignant or unspecified tumor (SMQ, narrow scope), hyperostosis, osteoarthritis, positively adjudicated adverse events of ONJ, AFF, and positively adjudicated serious CV events will be tabulated by PT and treatment group (see Appendix 13.5). Subcategories are added as appropriate (EG, MI, stroke and other CV events).

#### 10.2.4.1 Osteonecrosis of the jaw adjudication

The events of ONJ which occurred in the study will be adjudicated and the positively adjudicated ONJ will be summarized. All potential events of ONJ identified through a pre-defined search of the MedDRA® terms in the adjudication manual for ONJ will be submitted to the ONJ Adjudication Committee for blinded review and adjudication. The committee will determine whether the event meets the case definition criteria for ONJ.

#### Atypical femoral fracture adjudication 10.2.4.2

The events of AFF which occurred in the study will be adjudicated and the positive adjudicated AFF will be summarized. All potential events of AFF identified through a pre-defined search of the MedDRA® terms in the adjudication manual for AFF will be submitted to the AFF Adjudication Committee for blinded review and adjudication. The committee will determine whether the event meets the case definition criteria for AFF.

### 10.2.4.3 Adjudicated positive cardiovascular events

All deaths and potential cardiovascular-related serious adverse events (SAEs) as predefined search of the MedDRA® terms according to the adjudication manual for cardiovascular event will be submitted to an external independent committee comprised of experienced cardiologists for blinded adjudication. The committee will adjudicate the events and determine whether the event is cardiovascular in nature.

Baseline cardiovascular risk factors will be summarized descriptively as listed in Section 6.2.1.

Only events positively adjudicated by the adjudication committee to meet cardiovascular event definition criteria will be included for analyses. Positively adjudicated cardiovascular events of death, cardiac ischemic event, cerebrovascular event, non-coronary revascularization, heart failure and peripheral vascular events not requiring revascularization will be summarized using subject incidence rates, odds ratios and 95% confidence intervals. No statistical tests will be performed.

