In this Phase 3, multicenter, randomized, double-blind, ALN-controlled study, 4093 postmenopausal women with osteoporosis were randomized in a 1:1 ratio to receive either romosozumab 210mg sc QM (2046 subjects) or ALN 70mg orally (po) every week (QW) (2047 subjects) for 12 months. After the initial 12-month study period, all subjects received ALN while remaining blinded to their initial treatment assignment. The Primary Analysis was performed when clinical fracture events (comprising of nonvertebral fracture or clinical vertebral fracture) were confirmed for at least 330 subjects and all subjects had the opportunity to complete the Month 24 study visit.

The results at the time of the Primary Analysis (median observation time 33 months) demonstrated that treatment with romosozumab for 12 months followed by ALN significantly reduced the incidence of new vertebral fractures through 24 months (coprimary endpoint), clinical fractures (coprimary endpoint), and nonvertebral fractures (key secondary endpoint) in postmenopausal women with osteoporosis at high risk for fracture compared with ALN alone. At 24 months, subjects in the romosozumab treatment group had a statistically significant 50% reduction in the relative risk of a new vertebral (spine) fracture compared with those receiving ALN alone. At the time of the Primary Analysis, subjects in the romosozumab treatment group had a 27% reduction in the relative risk of clinical fracture and a 19% reduction in nonvertebral fractures, compared with those receiving ALN alone. A nominally significant reduction in hip fractures was also observed in subjects in the romosozumab treatment group.

Subject incidence of AEs and serious adverse events (SAEs) were generally well balanced between treatment groups in each study. In the 2 Phase 3 studies (20070337 and 20110142), the number of positively-adjudicated events of atypical femoral fracture (AFF) and osteonecrosis of the jaw (ONJ) was low. In 20110142, a numerical imbalance in the positively-adjudicated cardiovascular (CV) SAEs was observed between the romosozumab and ALN groups at 12 months. This imbalance was observed specifically for serious cardiac ischemic and

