cerebrovascular events, with a higher incidence in the romosozumab group compared with the ALN group (romosozumab: 0.8% for both events; ALN: 0.3% for both events). These findings were not observed at 12 months in the larger, placebo-controlled study in postmenopausal women with osteoporosis (20070337). A causal relationship between romosozumab and CV SAEs has not been established.

Across the studies, the benefit-risk profile of romosozumab is considered favorable. Treatment with romosozumab has demonstrated fracture risk reduction within 12 months, ongoing fracture risk reduction maintained with follow-on antiresorptive therapy, and robust improvement in BMD at the spine and the hip (including in subjects previously treated with antiresorptive therapy).

Further information on the studies mentioned above can be found in Section 5.4.

Refer to the Investigator's Brochure (IB) for more detailed information on romosozumab (eg, pharmacology, quality, nonclinical data, clinical data, and Reference Safety Information).

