# 2.5 Study design and conduct

This is a Phase 3 multicenter randomized, DBPC study followed by OL Treatment Period in postmenopausal Chinese women with osteoporosis to evaluate the efficacy, safety and tolerability of romosozumab treatment. The study consists of 4 study periods: Screening Period (Day -35 to Day -1), 6-month DBPC period, 6-month OL Treatment Period, and 3-month FU Period. The overall study design including treatment assignments is depicted in the schematic diagram in Figure 1. For each individual subject, the study will last approximately 16 months. A

03 Mar 2023 OP0002

subject's participation in the study may be extended up to 1 year after the final IMP administration if the subject tests positive for neutralizing antibodies to romosozumab at the EOS Visit or ET Visit.

[figure not shown]
In the DBPC Period, after screening, approximately 300 subjects will be randomized, stratified by age (<75 years,  $\ge 75$  years), in a 2:1 ratio to receive either 210 mg romosozumab subcutaneous (sc) treatment every month (OM) (200 subjects) or matched placebo sc OM (100 subjects) in a blinded manner for 6 months to evaluate if romosozumab treatment for 6 months. compared with placebo, is effective in increasing BMD, as assessed by DXA, at the lumbar spine, total hip, and femoral neck. The primary analysis will be performed using the data obtained from the DBPC Period.

Upon completion of the 6-month DBPC Period, subjects will enter the 6-month OL Treatment Period and receive 210mg romosozumab sc QM for 6 months in an open-label fashion. During this period, all subjects will receive active treatment (romosozumab), 12 months exposure for subjects randomised to romosozumab and 6 months exposure for those randomized to placebo.

After completing the OL Treatment period, subjects will be followed up for an additional 3 months (FU Period) and will complete the EOS Visit (Month 15). Subject participation in the study is concluded after the EOS Visit. Subjects who test positive for neutralizing antibodies to romosozumab at the EOS Visit or ET Visit will be asked to return for additional follow-up testing for up to 1 year after final administration of investigational medicinal product (IMP).

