# • Resulting sample size:

For the sample size calculations, a 2-group Satterthwaite t-test will be assumed (2-sided on a 5% significance level) which allows for unequal SDs and unequal sample size ratios. Taking into account the upper bounds pooled common SDs and the minimum effect size as assumptions (BMD of the femoral neck outlined above), the sample size of 146 subjects for romosozumab and 73 subjects for placebo would preserve at least 90% power for the percent change from baseline in BMD of the lumbar spine, total hip and femoral neck at Month 6.

To give a reasonable chance to show significance, at least 90% power for all 3 anatomical sites, following a hierarchical testing procedure (see Section 4.5) with safety objectives and dropout taken into account, a total sample size of 300 subjects (ie, 200 subjects in the romosozumab group and 100 subjects in the placebo group) seemed appropriate.

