#### Adverse events c 10.2

Treatment emergent AEs (TEAE) are defined as all AEs started or worsened in severity on or after the date of receiving first dose of IMP and before EOS date except lipid-type AEs starting on the date of first dose of IMP and not worsening (and not deemed IMP related by the investigator). Lipid-type AEs will be defined by the Dyslipidaemia SMQ (see Appendix 13.7). The different handling of lipid-type AEs starting on the date of first dose of IMP is to ensure that pre-existing lipid abnormalities are not reported as TEAEs (lipids are only measured at Day 1 before first IMP and not at Screening).

All subsequently described displays in Section 10.2 will be compiled for the DBPC Period and for the overall study period (treatment start through Month 15). For the displays on the DBPC Period, TEAEs with a start date before or on the End of DBPC period date will be included. For the overall period, TEAEs with a start date before or on the EOS date will be included.

Duration of AEs will not be calculated if there is missing stop date information. If the intensity of an AE is unknown, it is considered as severe. If the relationship to study drug is missing, it is considered as related. Note that if the seriousness of an adverse event is unknown, every attempt should be made to resolve this prior to a snapshot for an interim analysis or database lock; in the exceptional case that the seriousness of an adverse event is still missing then no imputation should be applied for this characteristic.

If a TEAE occurs on the date of switch from the DBPC period to the OL period, the event is attributed to the DBPC treatment. The only exception that TEAEs of injection site reactions (see Appendix 13.5), potentially related to hypersensitivity (Standardized MedDRA® Query [SMQ], narrow scope) will be in OL period.

The number and incidence of TEAEs will be summarized by treatment group, the MedDRA® SOC and PT with the SOC sorted alphabetically and within SOC the PT sorted by descending order of frequencies. The incidence of TEAEs will also be summarized by treatment group (including romosozumab total), intensity and relationship to IMP.

Adverse events will be presented as "number of participants (percentage of participants) [number of events]". In this style of output, "[number of events]" will include all cases of an AE including repeat occurrences in individual participants, while "number of participants" will count each participant only once.

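### The odds ratios planned for adjudicated CV events will usually rest on an empty arm, with no usable interval, and over the whole study would compare two romosozumab sequences

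*SAP*

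**What the plan says.** SAP 10.2.4.3 takes the events that the adjudication committee has confirmed, in six categories: death, cardiac ischemic, cerebrovascular, non-coronary revascularization, heart failure, and peripheral vascular events without revascularization. These "will be summarized using subject incidence rates, odds ratios and 95% confidence intervals". It adds: "No statistical tests will be performed". The section names no interval method, no continuity correction and no rule for an arm without events. It gives no odds ratio for all CV events combined and does not limit the comparison to one period.

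The periods come from SAP 10.2: "All subsequently described displays in Section 10.2 will be compiled for the DBPC Period and for the overall study period", the latter running from the start of treatment to Month 15. SAP 2.5 sets out a "6-month DBPC period, 6-month OL Treatment Period, and 3-month FU Period", with every subject on romosozumab in the open-label part. SAP 3.1 labels the final-analysis groups by sequence: placebo/romosozumab and romosozumab/romosozumab. SAP 2.6 settles on "a total sample size of 300 subjects (ie, 200 subjects in the romosozumab group and 100 subjects in the placebo group".

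Some per-arm information is given regardless. SAP 10.2.4 tabulates positively adjudicated serious CV events by preferred term and treatment group, and SAP 10.2.2 defines exposure-adjusted incidence rates with exact Poisson intervals.

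**The concern.** CV risk is a safety question that the protocol itself raises. Section 2.2 reports an imbalance in serious cardiac ischemic and cerebrovascular events in the alendronate-controlled study, section 5.1.1 asks for an individual CV risk assessment, section 6.2 excludes prior MI and stroke, and section 13.4.3.1 sends potential events to an independent committee. CV events are also the only adverse events for which the SAP names a between-group effect measure.

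That measure behaves badly when events are few. A sample odds ratio with an empty arm is 0 or infinite, and with two empty arms it is undefined. If this is the usual outcome, the trial ends without a usable interval on the CV difference, and how to handle empty cells is left to be decided after the data are unblinded. Over the whole study the same statistic compares two groups that have both received the drug, and a value near 1 could be taken to say more about drug versus no drug than it does.

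**Working it through.** **The plan's own figure.** The documents state no precision for the CV odds ratios. The size was set by BMD: 146 + 73 subjects for at least 90% power. For the femoral neck, with the lower bound 2.0 and SDs 4.39 and 4.10, SE = √(4.39²/146 + 4.10²/73) = 0.602 and 2.0/0.602 = 3.32. The Satterthwaite t-test then has 91.0% power, so the stated figure reproduces. It says nothing about rare events.

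**Inputs.**
- Arms: 200 and 100 (SAP 2.6).
- Rates per category: "romosozumab: 0.8% for both events; ALN: 0.3% for both events" (Protocol 2.2). These are 12-month rates; the imbalance "was observed between the romosozumab and ALN groups at 12 months".
- Placebo rate: not given. Of the placebo-controlled fracture study the protocol says only "These findings were not observed at 12 months in the larger, placebo-controlled study". The placebo rate is therefore an assumption, ranged here from 0.15% to 0.8%.
- Double-blind period: 6 months. Rates are used unscaled (12-month) and halved.

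**Chance of an empty arm, double-blind period, one category.** P(no event in an arm) = (1 − p)ⁿ. P(at least one arm empty) = 1 − [1 − (1 − p_R)²⁰⁰] × [1 − (1 − p_P)¹⁰⁰].

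| Romosozumab / placebo rate | Expected events | Romosozumab arm empty | Placebo arm empty | Both empty | At least one empty |
|---|---|---|---|---|---|
| 0.8% / 0.3% | 1.6 / 0.3 | 20% | 74% | 15% | 79% |
| 0.4% / 0.15% | 0.8 / 0.15 | 45% | 86% | 39% | 92% |
| 0.8% / 0.8% | 1.6 / 0.8 | 20% | 45% | 9% | 56% |
| 0.4% / 0.4% | 0.8 / 0.4 | 45% | 67% | 30% | 82% |
| 0.3% / 0.3% | 0.6 / 0.3 | 55% | 74% | 41% | 88% |
| 0.15% / 0.15% | 0.3 / 0.15 | 74% | 86% | 64% | 96% |

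With equal rates, the chance falls to 50% only at about 0.9% in both arms over six months, which is above the higher of the two 12-month rates.

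**What interval is left.**
- One event in all, in the romosozumab arm (1/200 versus 0/100). Given one event, P(it falls on romosozumab) = 200ψ/(200ψ + 100). Setting this to 0.025 gives ψ = (0.025 × 100)/(0.975 × 200) = 0.013, so the exact 95% interval is 0.013 to infinity.
- One event in all, in the placebo arm. By the same argument the interval is 0 to (0.975 × 100)/(0.025 × 200) = 19.5.
- No event in either arm: the data carry no information on the odds ratio.
- No empty arm, 2/200 versus 1/100: OR = (2 × 99)/(1 × 198) = 1.0; SE of the log = √(1/2 + 1/1 + 1/198 + 1/99) = 1.23; 95% CI 0.09 to 11.2.

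**Risk difference on the same data (Newcombe).**
- 1/200 versus 0/100: the Wilson limits are 0.09% to 2.78% and 0% to 3.70%. Difference 0.5%; lower limit 0.5 − √((0.5 − 0.09)² + 3.70²) = −3.2%; upper limit 0.5 + (2.78 − 0.5) = 2.8%.
- 0/200 versus 0/100: 0%, from −3.7% to 1.9%.

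**Overall period.** Assume the 0.8% and 0.3% annual rates apply on and off drug, and count off-drug time at 0.3% a year:
- romosozumab/romosozumab: 0.8% + 0.075% = 0.875%
- placebo/romosozumab: 0.15% + 0.4% + 0.075% = 0.625%

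A risk ratio of 0.8/0.3 = 2.7 in the double-blind period becomes 0.875/0.625 = 1.4 over the study. This is the dilution. At least one arm is empty with probability 61%; with equal 15-month rates it is 45% (1.0% in both) to 83% (0.375% in both).

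**The case against.** The SAP does not specify a Wald interval. An exact method gives an interval whenever at least one arm has an event, so it would be too strong to say that the odds ratio simply cannot be estimated. This stands in part: the interval exists but runs to 0 or to infinity, and no method is named.

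A reader might also infer that the trial would report nothing comparative on CV events. The documents do not support that. SAP 10.2.4.3 requires incidence in each arm, SAP 10.2.4 tabulates the events, and a reader could form a difference from the counts. What is not prespecified is an interval on that difference.

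A reader might take the overall period to be one in which both groups are on romosozumab throughout. It is not: it includes the six placebo-controlled months and the follow-up after the last dose at Month 11. Nor does any sentence ask for an overall-period CV odds ratio by name. The request follows from the general sentence in SAP 10.2, while the objectives for that period (SAP 2.2.3) are to characterize each sequence. The objection to the contrast, that it dilutes the drug effect, survives this.

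The rates are thin evidence. They cover two of six categories, against alendronate. An empty arm becomes less likely for a pooled endpoint: 57% if both categories are summed at 12-month rates (1.6% versus 0.6%), and 23% at 1.6% in both arms. The MI and stroke exclusions and the shorter period point the other way, towards lower rates.

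Finally, the alternative is imprecise too. The imbalance that prompts the question is 0.8% − 0.3% = 0.5 percentage points, and an interval reaching about 3 points either side of zero cannot confirm or exclude it. That is a limit of the trial's size, which no effect measure removes.

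**Conclusion.** The point holds for descriptive safety reporting. In the double-blind period, for a single CV category, the planned odds ratio has an empty arm in about 56% to 96% of trials across the assumed rates of 0.15% to 0.8%, and in 9% to 64% both arms are empty. The SAP then provides no usable interval on the between-group difference, although each arm's incidence is reported. In the overall period the chance of an empty arm is lower at the higher rates (45% at 1.0% in both), so the case there rests mainly on the contrast, which mixes six placebo-controlled months with a period after both groups have received the drug.

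These figures depend on an assumed placebo rate and on rates for two categories carried over to the rest. No test, primary or secondary conclusion is affected. It would go too far to say that a better measure would settle the CV question: it would bound the difference to within a few percentage points and no more.

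**What to change.** In SAP 10.2.4.3:

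- **Double-blind period.** Report the risk difference (romosozumab minus placebo) with a Miettinen-Nurminen or Newcombe 95% CI, for each CV category and for all adjudicated CV events combined. Both intervals are defined when arms are empty. An exact odds ratio may be kept as a supplement, with the method named.
- **Overall period.** Report incidence, or exposure-adjusted rates, for each sequence with exact 95% CIs, and no between-sequence odds ratio. SAP 10.2.2 already defines the exact Poisson interval. Time at risk in SAP 10.2.1 starts at the first romosozumab dose, so the events counted should come from the same time.

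The cost is about one sentence of SAP text and minor programming. Confirmatory testing and trial conduct do not change. The small downside is a departure from an odds-ratio format.
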